8.6.2 Secondary Safety Endpoints

Part 1 (Phase 1):

RP2D of cePolyTregs as assessed by cumulative safety, tolerability, pharmacodynamic and biomarker changes associated with administration of cePolyTregs compared with placebo/SOC

Parts 1 and 2:

Safety and tolerability of cePolyTregs as assessed by:

- Type and frequency of TEAEs
- Type and frequency of treatment-emergent serious adverse events (TESAEs)
- Type and frequency of adverse events of special interest (AESIs) including infusion/hypersensitivity reactions, increase in SARS-CoV-2 viremia, and infections including pneumonia and those involving pathogens not anticipated in a COVID-19 setting
- Type and frequency of changes in clinical laboratory values, physical examinations, electrocardiograms (ECGs), and vital signs

8.6.3 Secondary Efficacy Endpoints

Part 2 (Phase 2a):

Efficacy of cePolyTregs compared with placebo/SOC, as assessed by:

- The proportion of subjects with a 2-point or greater improvement in the WHO severity scale for COVID-19 pulmonary syndrome on each of Study Days 7, 14, 21, and 28
- The proportion of subjects with improvement in the WHO severity scale for COVID-19 pulmonary syndrome to Grade 3 or less on each of Study Days 7, 14, 21, and 28
- The proportion of subjects requiring mechanical ventilation on each of Study Days 7, 14, 21 and 28
- Number of days free of mechanical ventilation on Days 29 and 57
- Mean and median Sequential Organ Failure [SOFA] scores on each of Study Days 7, 14, 21 and 28
- Change in chest imaging (radiograph or CT scan) abnormalities
- All-cause mortality on Study Days 29 and 84

Parts 1 and 2:

Pharmacodynamic and biomarker changes associated with administration of cePolyTregs compared with placebo/SOC, including but not limited to:

- Change from baseline in circulating cePolyTregs
- Change from baseline in pulmonary cePolyTregs by endotracheal aspirate and mini BAL

UCSF	Clinical Study Protocol No. UCSF-cePolyTregs-01	Page 35 of 72
------	---	---------------

- Change from baseline in ferritin, C-reactive protein, LDH, and high-sensitivity troponin I (hs-TnI)
- Change from baseline in d-dimer
- Change from baseline in absolute lymphocyte count
- Change from baseline in C3, C4, and CH50
- Change from baseline in inflammatory cytokines/chemokines, e.g. IL-6, IL-12, IFN γ , TNF α , MCP-1 and MCP-4
- Phenotypic and functional changes from baseline in immune subsets using cytometric, genomic and/or proteomic analyses of cells harvested from endotracheal tubes, mini BAL, and blood

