11.8 Mechanical Ventilation Status

If the patient is receiving invasive mechanical ventilation, ventilatory parameters will be collected daily between 06:00 and 10:00, including the following, per local procedure:

Mode of ventilation, FiO₂(Fraction of inspired oxygen), SpO₂ , plateau pressure, peak pressure, PEEP (Positive End-Expiratory Pressure). If an ABG (arterial blood gas) is obtained during that time, then the PaO₂ (Partial pressure of arterial oxygen) will also be collected.

If the patient is receiving non-invasive ventilation, the level of inspiratory pressure, FIO₂, and PEEP will be registered. If the patient is receiving high-flow oxygen, the flow rate and the FIO₂ will be recorded.

The proportion of subjects requiring mechanical ventilation will be assessed on Study Days 7, 14, 21, and 28, and the number of days free of mechanical ventilation will be assessed on Days 28 and 56.

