11.13 Ventilator Procedures

Ventilator management, including weaning, shall follow the modified ARDS Network lower tidal volume (6 ml/kg PBW) protocol (Appendix A Ventilator Protocol). If not already being used, this low tidal volume protocol for mechanical ventilation shall be initiated within one hour of randomization. Since the time a subject achieves unassisted ventilation affects the co-primary endpoint, days free of ventilation, and because recent evidence-based consensus

recommendations have identified a best practice for weaning, weaning strategy will also be controlled by protocol rules in accordance with these evidence-based recommendations ([Appendix B Ventilator Weaning Procedure](#)). This will assure similar weaning methods and provide potential benefit to both study groups. This newer weaning strategy is a simplified version of the protocolized weaning strategy used in prior ARDS Network studies.

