13.3 Analysis Populations

13.3.1 Safety Population

The *safety population* consists of all subjects who receive any amount of study medication. All data summaries except PK-data related summaries will use this population.

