13.3.3 Efficacy Population

Subjects in the safety population who have at least 1 posttreatment assessment for a marker of clinical activity will be included in the efficacy population.

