13.8 Efficacy Analyses

Data will be summarized descriptively by treatment arm and overall. The descriptive summary for the categorical variables will include counts and percentages. Chi-squared tests (or Fisher's exact tests, as appropriate) will be used to compare categorical variables between study arms. Descriptive summaries for the continuous variables will include means, medians, standard deviations and minimum and maximum values. Two-sample t-tests (or Wilcoxon rank-sum tests, as appropriate) will be used to compare continuous variables between the two study arms. Time to recovery will be summarized using the Kaplan-Meier method and compared between study arms using the log-rank test.

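### The ventilation, ventilator-free-day and SOFA secondary endpoints have no rule for subjects who die, so they can favour the arm with more deaths or hide the excess

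*Combined protocol and SAP*

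**What the plan says.** Three of the Part 2 secondary efficacy endpoints in Section 8.6.3 are at issue:

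- The first concerns ventilator status at four fixed visits: "The proportion of subjects requiring mechanical ventilation on each of Study Days 7, 14, 21 and 28"
- The second counts time off the ventilator up to two cut-offs: "Number of days free of mechanical ventilation on Days 29 and 57"
- The third summarises organ dysfunction at the same four visits as the first: "Mean and median Sequential Organ Failure [SOFA] scores on each of Study Days 7, 14, 21 and 28"

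None mentions death. Section 11.8 restates the two ventilation endpoints without a death rule and with other cut-off days: "the number of days free of mechanical ventilation will be assessed on Days 28 and 56". Table 2 in Section 11.7 has no SOFA value for a subject who has died.

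Section 13.8 plans chi-squared or Fisher tests for categorical variables and, for continuous ones, "Two-sample t-tests (or Wilcoxon rank-sum tests, as appropriate) will be used to compare continuous variables between the two study arms". It names no analysis population. Section 13.3.1 sets a default, the safety population: "All data summaries except PK-data related summaries will use this population". Section 13.3.3 then defines a separate efficacy population among treated subjects, namely those "who have at least 1 posttreatment assessment for a marker of clinical activity will be included in the efficacy population".

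The one explicit analysis rule for death (Section 13.1) censors at Day 29 and applies to time to recovery only. The Synopsis and Section 13 leave analysis detail to a separate SAP, which the Synopsis requires before database lock. It is not among the documents supplied.

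**The concern.** Every subject is on mechanical ventilation at entry (Section 9.1, criterion 1), and Section 8.8.6 works with an anticipated mortality of 50%. Death is therefore a common outcome that ends ventilation and ends SOFA scoring. A patient who dies on the ventilator no longer requires it. Without a rule, that patient can move from the bad category to the good one on the ventilation endpoint, drop out of the SOFA mean, and perhaps gain ventilation-free days after death.

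At stake is a misleading secondary efficacy result: an apparent respiratory or organ-function benefit produced by deaths, or an excess of deaths that these endpoints fail to show. The status of ventilation-free days is also unsettled. Section 11.13 reads "Since the time a subject achieves unassisted ventilation affects the co-primary endpoint, days free of ventilation", whereas Section 8.6.1 does not list it as primary and Section 8.6.3 lists it as secondary.

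**Working it through.** **Is a rule present anywhere?** The plan gives no figure for these three endpoints, so there is none to reproduce; its 80% power concerns time to recovery. The first check is by reading.

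| Place | Rule for deaths on these endpoints |
|---|---|
| 8.6.3, 11.8 | None |
| 11.7, Table 2 | No score for death |
| 13.1 | Time to recovery only |
| 13.3.1, 13.3.3 | Overall populations; nothing on who is counted on each assessment day |
| 13.8 | Generic tests; no population named |
| 11.6, WHO scale | Death scores 8, which settles the WHO-scale proportions but not these three |

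**Illustration.** All counts are assumed except 50 per arm, which is from Section 13.2. Results are conditional on which patients die. Placebo has 26 extubated on Day 12, 16 dead and 8 still ventilated at Day 28. cePolyTregs has 24 dead, 8 more than placebo. Deaths are on Day 10 unless stated. P-values are Fisher exact; deaths of 16 versus 24 give p = 0.15.

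Ventilation-free days to Day 28 are 28 − 12 = 16 if extubated and 0 if still ventilated. A death on Day d gets 28 − d if days after death are credited, otherwise 0.

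*Case 1: the 8 excess deaths are in patients who would have stayed ventilated (treated: 26 extubated, 24 dead, 0 ventilated).*

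- Ventilated: 8/50 vs 0/50, p = 0.006. Survivors only: 8/34 vs 0/26, p = 0.008.
- Dead or ventilated: 24/50 vs 24/50.
- Days credited: (26×16 + 16×18)/50 = 14.08 vs (26×16 + 24×18)/50 = 16.96, a gap of 2.88 favouring the arm with more deaths. With deaths on Day 5 the gap is 8×23/50 = 3.68; on Day 25 it is 8×3/50 = 0.48.
- Death set to 0: 26×16/50 = 8.32 in both arms.
- With 6 excess deaths: ventilated 8/50 vs 2/50, p = 0.09; credited gap 6×18/50 = 2.16. With 4: 8/50 vs 4/50, p = 0.36; gap 1.44.

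*Case 2: the 8 excess deaths are in patients who would have been extubated (treated: 18 extubated, 24 dead, 8 ventilated).*

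- Ventilated: 8/50 vs 8/50, no difference. Survivors only: 8/34 (24%) vs 8/26 (31%), against the arm with more deaths.
- Dead or ventilated: 24/50 vs 32/50, so the excess shows.
- Days credited, deaths on Day 10: 14.08 vs (18×16 + 24×18)/50 = 14.40, which hides the excess. Deaths on Day 25: (26×16 + 16×3)/50 = 9.28 vs (18×16 + 24×3)/50 = 7.20, against the arm with more deaths.
- Death set to 0: 8.32 vs 18×16/50 = 5.76, a gap of 2.56 in the right direction for any day of death.

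**SOFA (separate assumed example).** Each arm has 30 subjects who would score 4 and 20 who would score 14. Arm B loses 10 of the sicker group, so its survivor mean is (30×4 + 10×14)/40 = 6.5.

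- Arm A loses all 20 of the sicker group: survivor mean 4.0, better than B despite twice the deaths. Scoring death at the maximum of 24 (6 systems × 4) gives A (30×4 + 20×24)/50 = 12.0 and B (30×4 + 10×14 + 10×24)/50 = 10.0, so the order reverses.
- Arm A loses 10 from each group: survivor mean (20×4 + 10×14)/30 = 7.3, worse than B. The direction again depends on who dies.

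**The case against.** The strongest reply is that counting deaths in secondary endpoints is ordinary SAP content, and the SAP was not supplied. That stands as a limit: the finding is that the rule is absent from the supplied text, not that nobody has written one. It does not remove the point, because these choices define what the endpoints measure and the Synopsis requires the SAP only before database lock.

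Several safeguards exist. The WHO-scale proportions in the same list score death as 8, so a death cannot count as improvement. All-cause mortality is an endpoint, and the DSMB reviews each death. These would reveal an imbalance in deaths but do not say how the three endpoints are computed.

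A reader might infer more than the documents support, in three ways:

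- *That these endpoints always favour the arm with more deaths.* Case 2 shows otherwise. The direction in Case 1 comes from holding extubations equal.
- *That there is no denominator at all.* Section 13.3.1 sets a default, and Section 13.3.3 needs only one posttreatment assessment, so a later death does not remove a subject. The actual gap is narrower: the two populations overlap, Section 13.8 does not choose between them, and whether a dead subject counts on a given day is unstated.
- *That the plan credits days after death.* Nothing says so. It is one possible reading, and arguably not the natural one; the text simply does not exclude it.

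It is also fair to say that the remedies below are choices among several defensible ones. The gap itself compels only that a rule and a population be stated.

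**Conclusion.** The point holds for the supplied text. Three Part 2 secondary endpoints, to be compared between arms in a fully ventilated population with 50% anticipated mortality, have no rule for death. Followed literally, they can favour the arm with more deaths when the excess falls on patients who would have stayed ventilated, and can hide or understate it when it falls on patients who would have been extubated.

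The size is conditional. In the assumed examples with 8 excess deaths per 50, the ventilated proportion ranges from 8/50 vs 0/50 (p = 0.006) to no difference. The credited ventilation-free-day difference ranges from 3.7 days in favour of the arm with more deaths to 2.1 days against it. The p-value of 0.006 is an extreme case that needs no treated subject still ventilated at Day 28; with 4 excess deaths it is 0.36.

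The consequence is confined to secondary results. Time to recovery has its own death rule, and the WHO-scale and mortality endpoints are unaffected. This should be corrected, but it does not invalidate the trial.

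**What to change.** State the following in Sections 8.6.3 and 13.8, or in the SAP before unblinding:

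1. Compare dead or on mechanical ventilation at Days 7, 14, 21 and 28, with the ventilation-only proportion and the deaths shown descriptively beside it.
2. Set ventilator-free days to 0 for anyone who dies by the cut-off day, and use the rank-sum test that Section 13.8 already allows.
3. Rank death worst in the between-arm SOFA comparison. Keep the listed mean and median as survivor-only description, with the number of deaths.
4. Name one analysis population for these endpoints and keep deaths in its denominator on every assessment day.

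Separately, reconcile the co-primary label in Section 11.13 with Sections 8.6.1 and 8.6.3, and the Day 29/57 cut-offs in Section 8.6.3 with Day 28/56 in Section 11.8.

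Cost: no new data, visits or subjects. The composite no longer isolates ventilator use, which is why the ventilation-only proportion stays as description. A change to Section 8.6.3 is a protocol amendment and needs IRB approval (Section 14.11).

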8.7 Cohort Dose Escalation

Part 1 of this study will use a cohort dose escalation design. Each cohort will initially enroll 3 subjects. If 0 of 3 evaluable subjects experiences a DLT (Section 8.8.3), then advancement to the next cohort may occur. If 1 of 3 subjects experiences a product-related DLT, then additional subjects will be enrolled in the same cohort for a total of up to 6 evaluable subjects. If 1 out of the 6 subjects experiences a product-related DLT, then advancement to the next cohort may occur. If 2 or more subjects in a cohort of up to 6 subjects experience a product-related DLT, no additional subjects will be enrolled in that cohort until a complete evaluation of all available data can be conducted and an opinion can be rendered by the DSMB as to whether the dose has exceeded the MTD. Dose escalation is allowed to proceed if no predefined stopping criteria are met.

Based on cumulative safety, tolerability, product manufacturing feasibility, and PD data from all Part 1 cePolyTregs cohorts (including biomarker data listed in [Table 4](#)), the RP2D will be determined for use in Part 2 of the study. The cePolyTregs RP2D will be received by 6 treated subjects in Part 1.

Part 1 cohort enrollment will proceed in a sequential manner to evaluate escalating dose levels of cePolyTregs. The first dose level to be studied will be 1×10^8 cells by IV infusion over approximately 1 hour and the maximum dose level to be studied will be 4×10^8 cells. An intermediate dose level of 2×10^8 cells is planned. Alternatively, an additional cohort at an intermediate dose may be added to better define the MTD and/or RP2D.

8.8 Data Safety Monitoring Board, Maximum Tolerated Dose Determination, Dose-Limiting Toxicity, and Stopping Criteria

8.8.1 Data Safety Monitoring Board

The DSMB membership will consist of independent medical experts with expertise in infectious disease, pulmonary medicine, and/or clinical research. The full details of the DSMB structure and responsibilities are provided in the DSMB Charter.

The RP2D determination will be made based on Part 1 (Phase 1) cohorts in which each new higher dose will be studied until the RP2D is identified; that RP2D will then be studied in Part 2 (Phase 2).

Dose escalation is allowed to proceed if no predefined stopping criteria are met. Dose escalation decisions will be based on the required number of subjects in a cohort completing the 7-day DLT assessment period. After the last subject in each cohort has completed the DLT assessment period, the DSMB will conduct a review of all available data (safety and tolerability) from both the current cohort and cumulative data from all cePolyTregs cohorts before determining recommendations for advancement to the next dose level. Details of cohort dose escalation are provided in Section 8.7.

Additional subjects may be enrolled in a cohort if considered necessary by the DSMB to further characterize product safety, tolerability, or efficacy. Also, the DSMB may recommend modification of the doses to be evaluated including de-escalation to a lower dose, to not initiate specific dose cohorts, to initiate additional dose cohorts, or to terminate the study if it is deemed necessary. If escalation is terminated, the next-lower dose may be declared the MTD and/or RP2D. Appropriate regulatory approvals will be obtained prior to initiation of any DSMB-recommended protocol changes, as required.

8.8.2 Maximum Tolerated Dose

The MTD is defined as the cePolyTregs dose below the dose at which 2 or more of 6 subjects receiving cePolyTregs in a Part 1 cohort experience a DLT, as confirmed by the DSMB.

8.8.3 Dose-Limiting Toxicities

A DLT is defined as any related TEAE \geq NCI CTCAE 5.0 Grade 3 in a subject who has received treatment with cePolyTregs which also represents a shift from baseline clinical status of \geq 1 NCI CTCAE grade.

Adverse events related to the standard of care (e.g., dexamethasone) are not considered DLTs. TEAEs related to ARDS will not be considered DLTs, unless they are judged to be related (or also related) to cePolyTregs.

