The Treatment Period will begin on Day 0 with randomization (Part 2 only) and administration of the investigational product (IP; cePolyTregs or placebo) and have a duration of 28 days. During the Treatment Period, subjects will be followed closely for outcomes to define the safety, tolerability, PD/biomarker changes, and efficacy of cePolyTregs. Subjects meeting clinical criteria for intra-hospital or inter-hospital transfer, as well as hospital discharge, will be followed according to the Schedule of Events (SOE) table irrespective of the location of the subject; ambulatory follow-up visits may be conducted at the study center or with in-home visiting study support staff. Following the Treatment Period, subjects will enter the Safety Follow-up Period.

Safety Follow-up Period

The Safety Follow-up Period will have a duration of 56 days, culminating with an end-of-study (EOS) visit on Day 84.

If subjects terminate early from the study for reasons other than death, they will be asked to undergo an Early Termination (ET) Visit within 7 days of their termination; the reasons for early termination will be documented. Since this is a single-dose study, subjects experiencing a product-related DLT will be asked to remain in the study and complete all study visits through the EOS visit. These subjects will not be replaced. If a subject terminates early for a reason other than a toxicity during the Treatment Period, the subject may be replaced at the discretion of the sponsor.

A DSMB will periodically convene and review all available clinical and laboratory data during the study. After its evaluation, the DSMB may recommend study continuation (with or without modification) or termination of a dose; the DSMB may also recommend de-escalation to a lower dose. If escalation is terminated, the next-lower dose may be declared the MTD and/or RP2D. Alternatively, an additional cohort at an intermediate dose may be added to better define the MTD and/or RP2D.

Dose Limiting Toxicity, Maximum Tolerated Dose, Dose Escalation Stopping Rules, and Individual Subject Stopping Rules:

A DLT is defined as any related TEAE of NCI CTCAE 5.0 grade ≥ 3 which also represents a shift from baseline clinical status of ≥ 1 NCI CTCAE grade.

The MTD is defined as the cePolyTregs dose below the dose at which 2 or more of 6 subjects receiving cePolyTregs in a Part 1 cohort experience a DLT, as confirmed by the DSMB.

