8.6 Endpoints

8.6.1 Primary Endpoints

Part 1 (Phase 1):

Safety and tolerability of cePolyTregs as assessed by DLTs, defined as any related treatment-emergent adverse event (TEAE) with an NCI CTCAE 5.0 grade ≥ 3 which also represents a shift from baseline clinical status of ≥ 1 NCI CTCAE grade.

Part 2 (Phase 2a):

Efficacy of cePolyTregs compared with placebo/SOC, as assessed by time to recovery, defined as the first day during the 28 days after randomization on which a subject meets the criteria for category 0, 1, 2, 3, or 4 on the WHO severity scale for COVID-19 pulmonary syndrome.

Safety of cePolyTregs as assessed by the occurrence of related TEAEs with an NCI CTCAE 5.0 grade ≥ 3 .

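### Section 8.8.3 drops standard-of-care-related events from the DLT count even when cePolyTregs may also have caused them

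*Combined protocol and SAP*

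**What the plan says.** The DLT definition appears four times. The synopsis gives it as a primary endpoint and again under the stopping rules: "A DLT is defined as any related TEAE of NCI CTCAE 5.0 grade" 3 or higher, with a worsening of at least one grade from baseline. Section 8.6.1 repeats it for the Part 1 primary endpoint: "Safety and tolerability of cePolyTregs as assessed by DLTs, defined as any related treatment-emergent adverse event (TEAE") meeting the same grade and shift conditions. None of these three mentions standard of care.

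Section 8.8.3 opens with the same definition, limited to subjects treated with cePolyTregs, and then adds two exclusions:

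- Standard of care: "Adverse events related to the standard of care (e.g., dexamethasone) are not considered DLTs".
- ARDS: "TEAEs related to ARDS will not be considered DLTs, unless they are judged to be related (or also related) to cePolyTregs".

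Section 8.7 uses the DLT count for escalation and cites 8.8.3: "If 0 of 3 evaluable subjects experiences a DLT (Section 8.8.3), then advancement to the next cohort may occur". It continues: "If 1 of 3 subjects experiences a product-related DLT, then additional subjects will be enrolled in the same cohort". With two or more in a cohort of up to 6, enrollment in that cohort is held for a DSMB opinion. Section 8.8.2 sets the MTD at the preceding dose once "2 or more of 6 subjects receiving cePolyTregs in a Part 1 cohort experience a DLT, as confirmed by the DSMB".

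**The concern.** The two exclusions in 8.8.3 treat shared causation differently. The ARDS sentence foresees an event with two causes and keeps it as a DLT if cePolyTregs is one of them. The standard-of-care sentence has no such condition, so taken at its word it removes an event that the investigator has judged related to the product.

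Such events are foreseeable. Sections 8.2 and 8.2.2 name infection as a potential effect of cePolyTregs and a class effect of immunomodulatory therapy. Section 11.14 lists steroids among the immunosuppressive therapies. A grade 3 infection in a subject on dexamethasone could reasonably be attributed to both.

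Two things are at stake. A 3+3 decision turns on single events in a first-in-human escalation (Section 8.2 reports no earlier clinical study of cePolyTregs). And the escalation tally under 8.8.3 and the Part 1 primary endpoint under 8.6.1 could classify the same subject differently.

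**Working it through.** The plan states no figure on this point, so there is none to reproduce. The check is a comparison of texts, followed by the effect of one omitted event on the tally.

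**Step 1. Classify one event under each text.** Take an event of grade 3 or higher, at least one grade worse than baseline, judged related to both cePolyTregs and dexamethasone. Under Section 12.5 it is recorded as related, because any possibility of a link to study medication is enough; a second cause does not remove it.

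| Text | DLT? |
|---|---|
| Synopsis, primary endpoint | Yes |
| Synopsis, stopping rules | Yes |
| Section 8.6.1 | Yes |
| Section 8.8.3, opening definition | Yes |
| Section 8.8.3, standard-of-care sentence, read literally | No |
| Section 8.8.3, ARDS sentence, if the second cause were ARDS instead | Yes |

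Section 12 makes an exception similar to the ARDS one: events expected in critically ill patients become reportable when considered related to study drug. No text extends that exception to standard-of-care events for the DLT count.

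**Step 2. Can the situation arise?** Section 10.1 gives all subjects in both parts standard of care including dexamethasone, so shared attribution is possible in any Part 1 subject.

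**Step 3. Which text governs escalation?** Sections 8.1.1 and 8.7 both cite 8.8.3. The DLT table in Section 13.6 does not say which wording it uses.

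**Step 4. Effect of one omitted event.** The exact one-sided 95% upper bound for x events in n subjects is the 0.95 quantile of Beta(x+1, n−x).

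| True tally | Upper bound | Action | Tally as read | Upper bound | Action |
|---|---|---|---|---|---|
| 1/3 (33%) | 0.865 | Expand to 6 | 0/3 (0%) | 0.632 | May advance |
| 2/6 (33%) | 0.729 | Hold for DSMB opinion | 1/6 (17%) | 0.582 | May advance |

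**Step 5. What a skipped expansion would forgo (illustration).** If 1/3 is read as 0/3, three further subjects are not enrolled before advancement. The chance that they would have shown at least one more DLT is 1 − (1−p)³. The documents give no DLT rate, so p is assumed:

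- p = 0.10: 1 − 0.90³ = 0.271
- p = 0.20: 1 − 0.80³ = 0.488
- p = 0.30: 1 − 0.70³ = 0.657
- p = 0.40: 1 − 0.60³ = 0.784

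**Step 6. Effect on the mechanical rule (illustration).** A cohort passes with probability (1−q)³ + 3q(1−q)²·(1−q)³, where q = p(1−f) is the counted DLT rate and f is the share of DLTs dropped. Both p and f are assumed.

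| p | f = 0 | f = 0.25 | f = 0.50 | f = 0.75 |
|---|---|---|---|---|
| 0.20 | 0.709 | 0.814 | 0.906 | 0.973 |
| 0.30 | 0.494 | 0.654 | 0.814 | 0.944 |
| 0.40 | 0.309 | 0.494 | 0.709 | 0.906 |

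Steps 5 and 6 ignore DSMB review and the Section 8.8.6 criteria. They show how sensitive the rule is; they do not predict what would happen in this trial.

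**The case against.** The best counter-argument is that the sentence excludes only events due to standard of care and not to the product. Several places support this. The synopsis and Sections 8.1.1, 8.7 and 8.8.5 speak of product-related DLTs. Section 12.5 classifies causality by study medication alone, and 12.6.1 records it only against study drug or study procedures. With no standard-of-care causality field, the plan describes no step for removing a related event. On this view the two sentences are merely unevenly drafted, and the shorter definitions elsewhere leave detail to 8.8.3, including the ARDS sentence. Section 13 also defers detail to a separate statistical analysis plan, and 8.8.1 to a DSMB charter; either could settle the wording.

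This reading is plausible and may be what was intended, but no text states it. The 0-of-3 rule and the MTD rule say only DLT, and the contrast with the ARDS sentence points the other way. The absence of a standard-of-care field also means that no listed adverse event attribute would show why an event had been left out.

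The safeguards are real. Advancement is permitted, not required, and before it "the DSMB will conduct a review of all available data (safety and tolerability) from both the current cohort and cumulative data" from all cohorts. The MTD needs DSMB confirmation. Section 8.8.6 has no standard-of-care exclusion, and qualifying respiratory infections are reported within 24 hours under 12.2. Six Part 1 subjects must receive the RP2D, so the Part 2 dose cannot rest on three. These measures limit the consequence without supplying a single definition for the DSMB to apply. The related-event triggers in 8.8.6 need a related death or two related grade 4 or 5 events, so one grade 3 DLT does not meet them. The infection trigger has no numerical threshold, and reporting an event as one of special interest does not make it a DLT.

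It is also fair that the bounds in Step 4 would apply to any miscounted event in any 3+3 trial. They give the consequence of an omission, not its frequency.

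**Conclusion.** The concern holds. Followed literally, 8.8.3 can remove from the escalation count an event that the synopsis, Section 8.6.1 and its own opening definition all count. One such event is enough to change a cohort decision, from expand to may advance or from hold to may advance.

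The conclusion rests on the literal reading and on at least one event being attributed to both causes. The frequency cannot be estimated from the documents and could be zero, and DSMB review keeps the practical risk limited. Under-counting of the primary endpoint is not claimed, because the 8.6.1 wording counts the event; what is unclear is whether the escalation count and the 13.6 table would agree with it. This should be fixed, with medium confidence: it is a small wording defect in a subject-protection rule.

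**What to change.** In Section 8.8.3, end the standard-of-care sentence with the exception that already closes the ARDS sentence, so that events judged related, or also related, to cePolyTregs remain DLTs. Have both synopsis definitions, Section 8.6.1 and the DLT summary in Section 13.6 refer to 8.8.3, so that one definition governs escalation, the primary endpoint and the table.

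The cost is one clause and a few cross-references. A cohort may occasionally expand to 6, or pause for a DSMB opinion, when under the literal wording it would not have. If the benign reading was always intended, nothing changes in practice and the doubt is removed for up to 12 centers.
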